9.1.2 Reporting Procedures for Adverse Events

The investigator is responsible for ensuring that all adverse events observed by the investigator or reported by the subject that occur after signing informed consent through the EOS are reported using the applicable eCRF (eg, Adverse Event Summary eCRF).

The investigator must assign the following adverse event attributes:

- Adverse event diagnosis or syndrome(s), if known (if not known, signs or symptoms),
- Dates of onset and resolution (if resolved),
- Severity [and/or toxicity per protocol],
- Assessment of relatedness to the device (prefilled AI/Pen or Personal Injector),
- Assessment of relatedness to investigational product (AMG 145) **and/or any study-mandated activity and/or procedure**, and
- Action taken.

The adverse event grading scale used will be the **National Cancer Institute** Common Terminology Criteria for AEs (**NCI-CTCAE**) grading scale. The toxicity grading scale used in this study is described in [Appendix B](#).

The investigator must assess whether the adverse event is possibly related to **IP** (AMG 145). This relationship is indicated by a “yes” or “no” response to the question: Is there a reasonable possibility that the event may have been caused by AMG 145?

The investigator must assess whether the adverse event is possibly related to the prefilled AI/Pen or Personal Injector used to administer IP. The relationship is indicated by a “yes” or “no” response to the question: Is there a reasonable possibility that the event may have been caused by the device?

The investigator must assess whether the adverse event is possibly related to any study-mandated activity or procedure. This relationship is indicated by a “yes” or “no” response to the question: Is there a reasonable possibility that the event may have been caused by a study activity/procedure?

The investigator is responsible for reviewing laboratory test results and determining whether an abnormal value in an individual study subject represents a clinically significant change from the subject’s baseline values. In general, abnormal laboratory findings without clinical significance (based on the investigator’s judgment) should not be recorded as adverse events. However, laboratory value changes that require treatment

or adjustment in current therapy are considered adverse events. Where applicable, clinical sequelae (not the laboratory abnormality) should be recorded as the adverse event.

The investigator's clinical judgment will be used to determine whether a subject should be removed from treatment or from the study due to an adverse event. A subject, or subject's parent/legal guardian, can also voluntarily withdraw from treatment due to an adverse event refer to [section 8.1](#) for additional instructions on the procedures recommended for safe withdrawal from treatment or the study. If the subject withdraws consent, the subject should be encouraged to undergo, at a minimum, an end-of-study assessment.

The investigator is expected to follow any reported adverse events until resolved, improved to baseline, or stabilized.

9.2 Serious Adverse Events

9.2.1 Definition of Serious Adverse Events

A serious adverse event (SAE) is defined as an adverse event that meets at least 1 of the following serious criteria:

- fatal
- life threatening (places the subject at immediate risk of death)
- requires in-patient hospitalization or prolongation of existing hospitalization
- results in persistent or significant disability/incapacity
- congenital anomaly/birth defect
- other medically important serious event

An adverse event would meet the criterion of "requires hospitalization", if the event necessitated an admission to a health care facility (eg, overnight stay).

If an investigator considers an event to be clinically important, but it does not meet any of the serious criteria, the event could be classified as a serious adverse event under the criterion of "other medically important serious event". Examples of such events could include allergic bronchospasm, convulsions, blood dyscrasias, drug-induced liver injury (see [Appendix B](#)) for drug-induced liver injury reporting criteria, or events that necessitate an emergency room visit, outpatient surgery, or urgent intervention.

If adverse events correspond to Grade 4 "life threatening" CTCAE grading scale criteria (eg, laboratory abnormality reported as grade 4 without manifestation of life threatening status), it will be left to the investigator's judgment to also report these abnormalities as

serious adverse events. For any adverse event that applies to this situation, comprehensive documentation of the event's severity status must be recorded in the subject's medical record.

9.2.2 Reporting Procedures for Serious Adverse Events

The investigator is responsible for ensuring that all serious adverse events observed by the investigator or reported by the subject that occur after signing of the informed consent through 30 days after the last dose of AMG 145 or EOS, whichever is later, are recorded in the subject's medical record and are submitted to Amgen. All serious adverse events must be submitted to Amgen within 24 hours following the investigator's knowledge of the event via the applicable serious adverse event report form.

After the protocol-required reporting period defined above, the investigator does not need to actively monitor subjects for serious adverse events. However, if the investigator becomes aware of a serious adverse event after this protocol-required reporting period, the investigator will report the event to Amgen within 24 hours following the investigator's knowledge of the event. Serious adverse events reported outside of the protocol-required reporting period will be captured within the safety database as clinical trial cases for the purposes of expedited reporting. The serious adverse event must be submitted to Amgen within 24 hours following the investigator's knowledge of the event via the applicable Serious Adverse Event Report Form. See [Appendix C](#) for a sample of the Serious Adverse Event Report Form.

The investigator must assess whether the serious adverse event is possibly related to IP (AMG 145). This relationship is indicated by a "yes" or "no" response to the question: Is there a reasonable possibility that the event may have been caused by AMG 145?

The investigator must assess whether the serious adverse event is possibly related to the prefilled AI/Pen or Personal Injector used to administer IP. The relationship is indicated by a "yes" or "no" response to the question: Is there a reasonable possibility that the event may have been caused by the device?

The investigator must assess whether the serious adverse event is possibly related to any other study-mandated activity or procedure. This relationship is indicated by a "yes" or "no" response to the question: Is there a reasonable possibility that the event may have been caused by a study activity/procedure?

The investigator is expected to follow reported serious adverse events until resolved, improved to baseline, or stabilized.

New information relating to a previously reported serious adverse event must be submitted to Amgen. All new information for serious adverse events must be sent to Amgen within 24 hours following knowledge of the new information. The investigator may be asked to provide additional follow-up information, which may include a discharge summary or extracts from the medical record. Information provided about the serious adverse event must be consistent with that recorded on the applicable CRF (eg, Adverse Event Summary CRF).

If a subject is permanently withdrawn from protocol-required therapies because of a serious adverse event, this information must be submitted to Amgen. To comply with worldwide reporting regulations for serious adverse events, the treatment assignment of subjects who develop serious, unexpected, and related adverse events may be unblinded by Amgen before submission to regulatory authorities. Investigators will receive notification of related serious adverse events reports sent to regulatory authorities in accordance with local requirements

Amgen will report serious adverse events and/or suspected unexpected serious adverse reactions as required to regulatory authorities, investigators/institutions, and IRBs/ECs in compliance with all reporting requirements according to local regulations and good clinical practice (GCP).

The investigator is to notify the appropriate IRB/EC of serious adverse events occurring at the site and other adverse event reports received from Amgen, in accordance with local procedures and statutes.

9.3 Pregnancy and Lactation Reporting

If a pregnancy occurs in a female subject, or a male subject **fathers a child**, while the subject is taking **AMG 145** and for an additional 15 weeks after the **last dose of** AMG 145, report the pregnancy to Amgen as specified below.

The pregnancy should be reported to Amgen's **Global Patient Safety** within 24 hours of the investigator's knowledge of the event of a pregnancy. Report a pregnancy on the Pregnancy Notification Worksheet ([Appendix D](#)). **Amgen's Global Patient Safety** will seek to **obtain pregnancy and birth outcome information**.

If a lactation case occurs while a female subject is taking **AMG 145** and for an additional 15 weeks after the **last dose of** AMG 145, report the lactation case to Amgen as specified below.

Any lactation case should be reported to Amgen's **Global Patient Safety** within 24 hours of the investigator's knowledge of the event. Report a lactation case on the Lactation Notification Worksheet ([Appendix D](#)).

10. STATISTICAL CONSIDERATIONS

10.1 Study Endpoints, Subsets, and Covariates

10.1.1 Primary Endpoint

Subject incidence of treatment emergent adverse events

10.1.2 Secondary Endpoints

- Percent change in LDL-C from baseline at each scheduled visit
- Percent change in non-HDL-C from baseline at each scheduled visit
- Percent change in Lp(a) from baseline at each scheduled visit
- Percent change in ApoB from baseline at each scheduled visit
- Percent change in total cholesterol/HDL-C ratio from baseline at each scheduled visit
- Percent change in ApoB/ApoA1 ratio from baseline at each scheduled visit
- Response rate of subjects with 15% or greater reduction in LDL-C by scheduled visit

10.1.3 Exploratory Endpoints

- Subject incidence of adjudicated events
 - death by any cause
 - cardiovascular death
 - myocardial infarction
 - hospitalization for unstable angina
 - coronary revascularization
 - stroke
 - transient ischemic attack (TIA)
 - hospitalization for heart failure
- Subject incidence of non-coronary revascularization

Lipid and other efficacy laboratory parameters:

- Percent change from baseline at each scheduled visit in
 - Total cholesterol
 - VLDL-C
 - HDL-C
 - ApoA1
 - Triglycerides

- Change from baseline at each scheduled visit in the following parameters:
 - LDL-C
 - Total cholesterol
 - non-HDL-C
 - ApoB
 - Total cholesterol/HDL-C ratio
 - ApoB/ApoA1 ratio
 - VLDL-C
 - HDL-C
 - ApoA1
 - Triglycerides
 - Lp(a)
 - PCSK9

Pharmacokinetics Endpoints

- Serum concentration of AMG 145 and PCSK9 at selected time points

10.1.4 Analysis Set

The evaluable analysis set (EAS) includes all subjects enrolled in this study. This analysis set will be used for all analyses.

10.1.5 Baseline Covariates

Baseline covariates include, but are not limited to:

- Age
- Gender
- Ethnicity or race
- LDL-C
- PCSK9
- Lipid modifying background therapy (eg statin, ezetimibe)

Subject's mutation status and apheresis status at baseline may be applied for subgroup analysis depending on the distribution of the subjects.

10.2 Sample Size Considerations

An approximate total of 310 subjects will enroll into this study such that the long-term safety, tolerability and efficacy of AMG 145 among subjects with severe familial hypercholesterolemia can be assessed.

The 95% confidence intervals for an approximate 5% incidence rate under various sample sizes using the binomial distribution for particular adverse events are provided in the table below:

Sample size	Total Number of Subjects Reporting Adverse Event	Estimated Adverse Event Incidence Rate	
		Incidence Rate	95% Confidence Interval
300	15/300	5%	(0.03, 0.07)
310	16/310	5.2%	(0.03, 0.08)
320	16/320	5%	(0.03, 0.07)

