#### 3.2 Sample Size

An approximate total of **310** subjects will enroll into this study such that the long-term safety, **tolerability** and efficacy of AMG 145 among subjects with severe familial hypercholesterolemia can be assessed. Enrollees will be comprised of subjects from study 20110233 or qualifying Amgen protocol as well as subjects with severe familial hypercholesterolemia due to genetic causes beyond those studied in the parent (eg, gain of function mutations in PCSK9). Finally, we will also include additional subjects with homozygous familial hypercholesterolemia. If these subjects are ineligible for participation into an AMG 145 protocol they may be considered for participation; they otherwise must wait after study 20110233 has been closed.

The 95% confidence intervals for an approximate 5% incidence rate under various sample sizes using the binomial distribution for particular adverse events are provided in the table below.

	Total Number of	Estimated Adverse Event Incidence Rate		
Sample size	Subjects Reporting Adverse Event	Incidence Rate	95% Confidence Interval	
300	15/300	5%	(3%, 7%)	
310	16/310	5.2%	(3%, 8%)	
320	16/320	5%	(3%, 7%)	

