#### 10. Statistical Methods of Analysis

## 10.1 General Principles

Statistical analyses in this open label, single arm study are descriptive in nature. No statistical inference or missing value imputation is planned. Subject disposition, demographics and baseline characteristics will be summarized.

Summary statistics for continuous variables will include the number of subjects, mean, median, standard deviation or standard error, 25th percentile (Q1), 75th percentile (Q3), minimum, and maximum. For categorical variables, the frequency and percentage will be given.

Final analyses will be based on data collected from this study. Descriptions of any integrated analyses with the parent studies are out of scope for this study.

The final analysis for the study will be performed at the end of the study (defined as when the last subject has completed the assessments for week 260 or until the investigator's recommendation of discontinuation, Amgen's recommendation of discontinuation, the subject's decision to discontinue for any reason, or until an administrative decision is made to close the study). At that time, the database will be cleaned, processed and locked. All endpoints will be analyzed based on this snapshot.

For the interim analysis, subjects were summarized by the 20110233 parent rollover/non-20110233 parent rollover and assigned treatment groups in 20110233 (AMG 145 or placebo) if applicable. However, for the final analysis, subjects will be summarized based only on the apheresis status at **enrollment** when applicable described in section 6.3.

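### Do the sample-size confidence intervals overstate the planned precision because they are not exact binomial intervals?

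*Protocol*

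**What the plan says.** Protocol 10.2 states that "An approximate total of 310 subjects will enroll into this study", so that long-term safety, tolerability and efficacy can be assessed. It then illustrates precision for an adverse event with an incidence near 5%, saying that "95% confidence intervals for an approximate 5% incidence rate under various sample sizes using the binomial distribution for particular adverse events are provided" in a table. The rows are 15/300 with (0.03, 0.07), 16/310 with (0.03, 0.08) and 16/320 with (0.03, 0.07). SAP 3.2 repeats the sentence, "The 95% confidence intervals for an approximate 5% incidence rate under various sample sizes using the binomial distribution", and the same limits as whole percentages. Neither document names the type of interval (exact, score or Wald).

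On analysis, SAP 10.1 says: "No statistical inference or missing value imputation is planned". It gives frequency and percentage for categorical variables. SAP 10.5.1 tabulates the incidence of treatment-emergent adverse events without confidence intervals.

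**The concern.** A reader who takes the reference to the binomial distribution literally will compute exact intervals and find an upper limit of 8% in every row, where two rows print 7%. The table also looks odd on its face: from 300 to 310 subjects the printed interval widens from 4 to 5 points, and at 320 it narrows again.

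The primary endpoint is adverse event incidence in a single-arm study, so the upper limit matters most: it shows which rates the data could exclude. The table is the only quantitative content in the two sample-size sections. If it overstated the precision of the planned trial, readers would expect more from 310 subjects than the study can give. In addition, the SAP plans no such interval in the adverse event tables, so the precision shown at planning has no counterpart in the reported results.

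**Working it through.** **Inputs** (Protocol 10.2, repeated in SAP 3.2): 15/300 = 5.00%, 16/310 = 5.16%, 16/320 = 5.00%. The confidence level is 95%, taken as two-sided because both limits are printed.

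**Step 1: reproduce the printed figures.** Wald interval: p ± 1.96 × √(p(1 − p)/n).

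- 15/300: 0.0500 ± 1.96 × 0.01258 = 0.0253 to 0.0747, which rounds to (0.03, 0.07).
- 16/310: 0.0516 ± 1.96 × 0.01257 = 0.0270 to 0.0762, which rounds to (0.03, 0.08).
- 16/320: 0.0500 ± 1.96 × 0.01218 = 0.0261 to 0.0739, which rounds to (0.03, 0.07).

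All six printed limits match under ordinary two-decimal rounding. There is no rule of rounding inward: the upper limit at 310 moves outward, from 0.0762 to 0.08.

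**Step 2: exact and score intervals.** Clopper-Pearson limits are the 2.5% quantile of Beta(x, n − x + 1) and the 97.5% quantile of Beta(x + 1, n − x).

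| Row | Printed | Wald | Exact | Wilson |
|---|---|---|---|---|
| 15/300 | 3% to 7% | 2.53% to 7.47% | 2.83% to 8.11% | 3.05% to 8.08% |
| 16/310 | 3% to 8% | 2.70% to 7.62% | 2.98% to 8.25% | 3.20% to 8.22% |
| 16/320 | 3% to 7% | 2.61% to 7.39% | 2.88% to 7.99% | 3.10% to 7.97% |

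In whole percentages, the exact and Wilson intervals both print as 3% to 8% in every row. Only the upper limits at 300 and 320 would change. The row for the planned size would not.

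**Step 3: size of the difference, like for like.** Widths, Wald against exact:

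- n = 300: 4.93 against 5.29 points; 1 − 4.93/5.29 = 6.8% narrower.
- n = 310: 4.93 against 5.27 points; 1 − 4.93/5.27 = 6.5% narrower.
- n = 320: 4.78 against 5.11 points; 1 − 4.78/5.11 = 6.5% narrower.

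Setting the printed 4 points against the unrounded exact widths gives 1 − 4/5.29 = 24% at 300 and 1 − 4/5.11 = 22% at 320. Most of that shortfall comes from printing whole percentages, not from the method. The dip from 8% to 7% between rows has the same source: unrounded, the Wald upper limits at 300 and 310 differ by only 7.62 − 7.47 = 0.15 points but fall on either side of 7.5%.

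**Step 4: does anything depend on these limits?** Neither document sets a target width or a rate to be excluded. SAP 3.2 describes 310 by who will be enrolled: subjects from Study 20110233 or another qualifying protocol, subjects with other genetic causes, and additional homozygous subjects. The protocol's amendment rationales link earlier increases to patient interest (Amendment 1) and to high-need subjects (Amendment 3). No stopping rule or analysis uses the table.

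**The case for a change.** The strongest case for a change is that 7% is not a 95% upper limit under the binomial distribution. If the true rate were 7%, the probability of 15 or fewer events in 300 would be 10.3%, and of 16 or fewer in 320 it would be 9.4%; a two-sided 95% limit should leave about 2.5%. The slip stands in both documents, correction would cost almost nothing, and a descriptive interval beside the adverse event rates would not conflict with a plan that makes no inference.

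The arithmetic in that case stands: two upper limits are about a point lower than an exact method gives. The wording is looser than the objection needs, however. A normal approximation with binomial variance p(1 − p)/n can pass under a general reference to the binomial distribution, so this is imprecise labelling more than a false statement. The affected rows are not the planned trial. Adding intervals to the adverse event tables is a separate preference. The sample-size table concerns a particular event near 5%, not overall incidence, and both documents consistently plan a descriptive analysis, so leaving intervals out contradicts nothing.

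**Conclusion.** A clerical matter of presentation; no change to the plan follows. The printed limits are Wald intervals under a loose label. An exact or Wilson method would print 8% instead of 7% as the upper limit at 300 and 320, and would leave the planned row (16/310, 3% to 8%) as it is. The method itself narrows the interval by about 7% of its width. The claim that the planned precision is overstated does not hold at 310, and no sample size, decision, analysis or conclusion depends on the other two rows.

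This rests on two-sided intervals, on 310 being the planned size (as both documents state), and on the table being an illustration and not the derivation of that size. An analyst who wants an interval for a particular event can compute one directly from the reported counts.

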10.3 Interim Analysis and Early Stopping Guidelines

There will be periodic interim analyses performed during this 5 year open label study. The study is not anticipated to stop early unless a major unexpected safety signal is detected.

10.4 Planned Methods of Analysis

10.4.1 General Approach/Considerations

Statistical analyses in this open label study are descriptive in nature. No statistical inference or missing value imputation is planned. **The final analysis for the study will be performed at the end of the study (defined as when the last subject has completed the assessments for week 260 or until the investigator's recommendation of discontinuation, Amgen's recommendation of discontinuation, the subject's decision to discontinue for any reason, or until an administrative decision is made to close the study).**

Subject disposition, demographics and baseline characteristics will be summarized.

Summary statistics for continuous variables will include the number of subjects, mean, median, standard deviation or standard error, minimum, and maximum. For categorical variables, the frequency and percentage will be given.

Subjects will be summarized according to whether subject rolled over from a parent study and their treatment allocation from a parent study when applicable.

For efficacy analyses, the baseline value is defined as:

- Subjects that participated in a qualifying parent study (including 20110233) and with baseline data from the parent study: the baseline is defined as the baseline of the qualifying parent study
- Subjects not enrolling from a parent study or without baseline data from the parent study: the baseline is defined as the baseline in this study

For non-efficacy analyses, baseline values for all subjects are defined as this study baseline values.

The percent change and absolute change from baseline in laboratory based exploratory endpoints at each scheduled visit will be summarized. Summaries of vital signs, ECGs, and anti-AMG 145 antibodies will be also provided.

10.4.2 Analysis of Key Study Endpoints

10.4.2.1 Primary Endpoint Analyses

Adverse events are coded using the latest version of Medical Dictionary for Regulatory Activities (MedDRA). Subject incidences of treatment-emergent adverse events, serious adverse events, and adverse events leading to withdrawal will be tabulated by system organ class and preferred term.

